#### **Causality**

Related: An AE classified as related may be either definitely related or possibly related where a direct cause and effect relationship with the medical device or study procedure has not been demonstrated, but there is a reasonable possibility that the AE was caused by the medical device or study procedure.

Not Related: An AE classified as not related may either be definitely unrelated or simply unlikely to be related (i.e., there are other more likely causes for the AE).

The study sponsor will assess the AEs and may upgrade the investigator's assessment of seriousness and/or causality. The study sponsor will notify the investigator of any AEs that is upgraded from non-serious to serious or from unrelated to related.

# 11.6 Return Product Analysis

Study sponsor representatives and their contact information are provided in the MOP that accompanies this protocol.

Alcon study products associated with device deficiencies and/or product related AEs should be returned under conditions described in the MOP.

# 11.7 Unmasking of the Study Treatment

Masked information on the identity of the assigned medical device should not be disclosed to the masked assessor or to the subject during the study. Refer to Section 9.5 of the protocol. If the treatment code needs to be broken in the interest of subject safety, the investigator is encouraged to contact an appropriate study sponsor representative prior to unmasking the

information if there is sufficient time. Dependent upon the individual circumstances (i.e., medical emergency), the code may be broken prior to contact with the study sponsor. The study sponsor must be informed of all cases in which the code was broken and of the circumstances involved. Additionally, the study sponsor may be required to unmask the information in order to fulfill expedited regulatory reporting requirements.

# 11.8 Follow-Up of Subjects with Adverse Events

The investigator is responsible for adequate and safe medical care of subjects during the study and for ensuring that appropriate medical care and relevant follow-up procedures are maintained after the study.

The investigator should provide the study sponsor with any new safety information (which includes new AEs and changes to previously reported AEs) that may affect the safety evaluation of the device. For AEs that are unresolved/ongoing at time of subject exit from study, any additional information received at follow-up should be documented in the eCRFs up to study completion (i.e., database lock). Any additional data received up to 6 months after subject has completed the study should be documented and available upon the study sponsor's request.

All complaints received after this time period will be considered and processed as spontaneous (following the post-market vigilance procedures) and should be communicated to the medical device's manufacturer as per local requirements. The investigator should also report complaints on non-Alcon products directly to the manufacturer as per the manufacturer's instructions or local regulatory requirements.

# 11.9 Pregnancy in the Clinical Study

Pregnancy is not reportable as an AE; however, complications may be reportable and will be decided on a case—by-case basis.

#### 12 ANALYSIS PLAN

All study conduct, effectiveness, and safety data will be reported for each sub-study (A and B) separately.

The primary time point of interest is 2 Months (Visit 3A) postoperative. After all subjects complete the 2-Month Visit (Visit 3A), the study database will be locked to conduct final inferential analyses. The study will be continued until all subjects complete the 6-Month Visit (Visit 4A), at which time the study database will be considered final and locked to report longer term effectiveness and safety results.

# 12.1 Subject Evaluability

Subject evaluability must be determined prior to breaking the code for masked treatment assignment and locking the database, based upon the deviations and evaluability plan. Subjects will be randomized to sub-study (A or B) and contralateral treatment in a 1:1 ratio to receive the investigational products.

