# 9.5 Treatment Masking

This study is assessor-masked and subject-masked.

Alcon personnel (including biostatistics, masked data manager, and clinical project lead) will also be masked. All other members associated with the study (at the site and the study sponsor) are unmasked.

Alcon personnel will be masked to IOLs implanted in the eye until the 2nd interim study database lock. At the 1st interim analysis, unmasking of Alcon personnel will be limited to the subset of subjects included in the 1st interim lock as needed. Masked assessors will be masked to the IOLs implanted until the final database lock.

Subjects will be provided with implant cards by unmasked personnel upon exiting the study and will become unmasked at that time.

Masked study personnel must avoid seeking information that may compromise masking. Unmasked study personnel must not disseminate information that is potentially unmasking to any masked personnel. The masked and unmasked site personnel must coordinate all study activities as necessary to protect masking and minimize bias during the study.

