1.4 Masking

This study is assessor-masked and subject-masked.

. Alcon personnel (including biostatistics, masked data manager, and clinical project lead) will also be masked. All other members associated with the study (at the site and the study sponsor) are unmasked.

At the 1st interim lock, unmasking of Alcon personnel will be limited to the subset of subjects who complete the 2-Month postoperative visit for inclusion in the 1st interim analysis. For those subjects not included in the 1st interim analysis, Alcon personnel will remain masked to IOLs implanted in the eye until the 2nd interim study database lock. Masked assessors will be masked to the IOLs implanted until the final database lock.

Subjects will be provided with implant cards by unmasked personnel upon exiting the study and will become unmasked at that time.

Masked study personnel must avoid seeking information that may compromise masking. Unmasked study personnel must not disseminate information that is potentially unmasking to any masked personnel. The masked and unmasked site personnel must coordinate all study activities as necessary to protect masking and minimize bias during the study.

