1.5 Interim Analysis

Two interim analyses are planned for this study.

The first interim analysis will be conducted when approximately 40 subjects (approximately 20 in each sub-study, minimum 30 subjects total) complete the 2-Month postoperative visit. This interim analysis is designed to review preliminary safety and effectiveness results for strategic business decision making purposes. There is no intention of stopping the study early. A second interim analysis will be conducted when all subjects complete the 2-Month postoperative visit, at this point treatment arms will be unmasked, and all inferential analysis will be conducted. To control the overall type I error rate (at one-sided alpha = 0.05) the Lan-DeMets method with an O'Brien-Fleming alpha spending function will be utilized to distribute the type I error rate between the first and second interim analyses. The first interim analysis will be conducted when approximately 1/3 of the information fraction (in this case 1/3 of the target sample size) is available, therefore for administrative purposes a one-sided alpha of approximately 0.001 will be spent at the first interim analysis and accordingly the

significance level at the second interim analysis (which is the primary inferential analysis point) will be one-sided 0.049 for all effectiveness endpoints. The power estimates provided below are based on a one-sided 0.049 significance level.

A final analysis will be performed once the 6-Month follow-up is complete, at which time the study database will be considered final and locked to report longer term effectiveness and safety results.

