2 ANALYSIS SETS

All eligible subjects will be screened to determine if they meet all inclusion and no exclusion criteria. Subjects who provide informed consent will be considered enrolled in the study. Evaluability of all subjects will be determined before database lock.

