2.1 Effectiveness Analysis Sets

There will be two effectiveness analysis datasets for each sub-study: the all-implanted analysis set and the best-case analysis set.

The all-implanted analysis set (AAS) will include all subjects with successful test and comparator article contralateral implantation, with at least one postoperative visit (same postoperative visit for both eyes).

The best-case analysis set (BAS) will include all subjects with successful contralateral implantation with the test and comparator article that had:

- At least one postoperative visit (same postoperative visit for both eyes),
- No preoperative ocular pathology or macular degeneration at any time in either eye, and
- No major protocol deviations

Subjects who become pregnant at any time during the study will also be excluded from the BAS.

The primary analysis set for effectiveness analyses will be the AAS,	
	I

All effectiveness analyses will be conducted on an as-treated basis. Eyes will be categorized under the actual study IOL implanted.

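### Can analysis-set membership change after unmasking, and would that undermine the two-month result?

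*Protocol*

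**What the plan says.** On timing, Protocol 12.1 states that "Subject evaluability must be determined prior to breaking the code for masked treatment assignment and locking the database", on the basis of a separate deviations and evaluability plan. SAP section 2 is shorter: "Evaluability of all subjects will be determined before database lock". It does not say which of the three locks (first interim, second interim, final) is meant.

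On masking, Protocol 9.5 states that "Alcon personnel (including biostatistics, masked data manager, and clinical project lead) will also be masked". SAP 1.4 then allows an exception: "At the 1st interim lock, unmasking of Alcon personnel will be limited to the subset of subjects who complete the 2-Month postoperative visit". Protocol 9.5 adds that this unmasking happens only as needed. Full unmasking comes later. SAP 1.5 says: "A second interim analysis will be conducted when all subjects complete the 2-Month postoperative visit, at this point treatment arms will be unmasked". Masked assessors stay masked until the final lock.

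On the sets, SAP 2.1 makes the AAS primary. It requires successful implantation of both lenses and at least one postoperative visit common to both eyes. The BAS adds three conditions: "No preoperative ocular pathology or macular degeneration at any time in either eye", no major protocol deviations, and "Subjects who become pregnant at any time during the study will also be excluded from the BAS". SAP 4.1.2 and 4.2.2 call the BAS analysis supportive and run it only when excluded eyes exceed 10% of the AAS.

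**The concern.** Fixing evaluability before the code is broken stops anyone from choosing exclusions while knowing which eye has which lens. Two parts of the plan seem to defeat that.

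First, subjects in the first interim also enter the two-month inferential analysis. Neither document says in terms that their evaluability is frozen before sponsor staff see their assignments.

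Second, two BAS criteria have no time limit short of study end, and the deviation criterion has none at all. The only scheduled postoperative dilated fundus examination is at Visit 4A, months after Visit 3A. Read literally, the BAS for the two-month analysis cannot be final when the arms are unmasked.

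If this reached the primary test, staff who knew the assignments could influence which pairs count. Even if confined to the BAS, it could change the supportive result, or whether that analysis is run, and the second-interim and final reports could differ.

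**Working it through.** **Inputs.** First interim: about 40 subjects, about 20 per sub-study, minimum 30 in total (Protocol 12.7, SAP 1.5). Randomized: 132; evaluable at two months: about 60 per sub-study, so 120 in total (Protocol 12.8, SAP 7). SD 0.08, expected difference 0, margin 0.1 logMAR (Protocol 12.8). One-sided level 0.049 (SAP 1.5). Visit windows: Visit 3A Day 45–70, Visit 4A Day 180–210 (Protocol Table 3-1).

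**1. The plan's own figures.**
- Share at the first interim: 40/120 = 33.3%, which reproduces the stated one third. Against those randomized it is 40/132 = 30.3%. At the minimum size it is 30/120 = 25.0% or 30/132 = 22.7%.
- Power: noncentrality = 0.1 × √60 / 0.08 = 9.68 against a critical t of 1.681, giving power above 99.9%, as stated. This also holds if 0.08 is read as a per-eye SD with uncorrelated eyes (0.08 × √2 = 0.113).

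**2. How late the BAS criteria run.** The gap from Visit 3A to Visit 4A is 180 − 70 = 110 to 210 − 45 = 165 days. Earlier fundus examinations are possible only at unscheduled visits. This part of the concern is correct.

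**3. Which sets can move after unmasking.**

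| Set | Membership rests on | Settled by | Can it move later? |
|---|---|---|---|
| AAS (primary) | Both lenses implanted, one shared postoperative visit | Visit 3A at the latest for anyone contributing two-month data | No |
| Safety set | Attempted implantation | Surgery | No |
| BAS (supportive) | AAS conditions plus pathology, pregnancy, deviations | Not stated | Yes |

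Everyone in the first interim has completed Visit 3A, so AAS membership is known before unmasking.

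**4. What it takes for a BAS analysis to exist.** With 60 subjects there are 120 eyes, and 10% is 12 eyes. Exclusion is by subject (two eyes), so 6 subjects give exactly 12, which does not exceed 10%; 7 give 14, which does. With 66 subjects, 10% of 132 is 13.2 eyes, and again 7 are needed.

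**5. Size of the possible shift.** Suppose the 3 least favourable of 60 pairs were dropped. The mean of the top 5% of a normal distribution is 2.06 SD = 2.06 × 0.08 = 0.165, so the shift is −3 × 0.165 / 57 = −0.0087; simulation gives about −0.0084. If the choice is limited to the roughly 20 pairs unmasked early, simulation gives about −0.006. But 3 exclusions alone are below the trigger of 7, so no BAS effectiveness result would be produced.

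**6. Comparison with the decision threshold.** At a true difference of 0 the expected upper limits are:
- n = 60: 1.681 × 0.08 / √60 = 0.0174
- n = 53 (7 excluded): 0.0185
- n = 40 (all 20 early-unmasked subjects excluded): 0.0214

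All are far below 0.1. For the AAS to be near failure, the observed mean would have to approach 0.1 − 0.0174 = 0.0826. That is 0.0826 / (0.08/√60) = 8.0 standard errors from the planned difference of 0.

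**The case for a change.** The strongest case for a change starts from the BAS being the main planned check of the AAS against deviations and pathology. Its trigger of 7 subjects is below the roughly 20 per sub-study unmasked early, so late calls could decide whether it is run as well as what it shows. Suppose the true difference sits exactly at the 0.1 margin and someone deliberately drops the worst k of those 20 pairs. The chance of a false noninferiority finding in the BAS is then about 0.048 at k = 0, 0.08 at k = 1, 0.15 at k = 3 and 0.26 at k = 7. SAP section 4 also speaks of evaluable subjects and eyes in general, so evaluability decisions are not visibly confined to the BAS. Clarifying the wording would cost little.

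Part of this stands. Neither document gives a BAS data cut-off or states that the interim subset is frozen before it is unmasked. The rest carries less weight:

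- The false-positive rates assume deliberate selection at the margin and bound the effect of discretion; they do not predict it. They concern the BAS, while the SAP's success criterion is tied to the AAS.
- Macular degeneration and pregnancy are clinical facts reported by sites. Macular degeneration and current or intended pregnancy are excluded at entry, and nothing in the documents suggests that late cases would approach 7 per sub-study. Major deviations do leave room for judgement, but Protocol 12.1 assigns them to the deviations and evaluability plan, which is not among the documents and may set staged sign-off.
- Protocol 12.1, SAP 2 and SAP 1.4, which calls the first interim a lock, can be read together as requiring evaluability of that subset before its own unmasking. A new sentence would largely repeat that.
- Protocol section 12 describes the two-month lock as serving the final inferential analyses and the last lock as serving longer-term results. No rerun of the two-month BAS analysis is planned.
- Having already-unmasked staff run the first interim is more than a wording change, because biostatistics is among the masked roles and the documents do not show an unmasked statistician.

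**Conclusion.** The plan leaves a detail unstated, and no change is needed. The BAS criteria do outlast the unmasking, and up to about a third of subjects (about a quarter at the minimum interim size) may be unmasked early to sponsor staff. But membership of the primary set is settled before that happens, and visual acuity is measured by assessors who stay masked to the end. What can move is a supportive analysis that needs at least 7 excluded subjects per sub-study to be run at all. Under the planned assumptions its upper limit would be about 0.019 logMAR, against a margin of 0.1.

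An analyst producing the two-month BAS result at the second interim has only the data in that lock, so a cut-off at that point is the natural working rule. The conclusion assumes that the AAS is applied as defined, that the SD and difference are near 0.08 and 0, and that late site-reported exclusions are uncommon. If the true difference were close to the margin, BAS exclusions would deserve close scrutiny, but the AAS result would still determine success.

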# 12.2 Analysis Sets

There will be three analysis datasets for each sub-study: the all-implanted analysis set, the best-case analysis set, and the safety analysis set.

[figure not shown]
The all-implanted analysis set (AAS) will include all subjects with successful test and comparator article contralateral implantation, with at least one postoperative visit.

The best-case analysis set (BAS) will include all subjects with successful contralateral implantation with the test and comparator article that had:

- At least one postoperative visit,
- No preoperative ocular pathology or macular degeneration at any time in either eye and
- No major protocol deviations

Subjects who become pregnant at any time during the study will also be excluded from the BAS.

All eyes with attempted test or comparator article implantation (successful or aborted after contact with the eye) will be considered evaluable for the Safety Set (SAS).

All effectiveness analyses will be conducted on an as-treated basis. Eyes will be categorized under the actual study IOL implanted.

# 12.3 Demographic and Baseline Characteristics

Demographic and baseline characteristics will be summarized for each sub-study on the subject and eye level (by treatment) as applicable. Counts and percentages will be presented for categorical variables such as sex, age group, race, and ethnicity. N, mean, standard deviation, median, minimum, and maximum will be presented for continuous variables that are collected at baseline such as age, eye biometry, monocular VA, and refractive errors.

# 12.4 Effectiveness Analyses

In general, descriptive statistics will be generated using mean, standard deviation, median, minimum, and maximum, for continuous variables. The number in each category and percentage will be reported for categorical variables. Summaries of logMAR VA may include two-sided 95% confidence intervals for the mean difference between treatment groups.

For statistical inference testing, the overall Type I error will be maintained, within each substudy, at the alpha 0.05 level (one-sided) using a sequential testing approach that will be detailed in the statistical analysis plan.

See Appendix B for specific effectiveness analyses related to sub-study A and see Appendix C for specific effectiveness analyses related to sub-study B.

# 12.5 Handling of Missing Data

There will be no imputation of missing data.

# 12.6 Safety Analyses

The safety objective for this study is to describe the incidence of ocular AEs including SSIs.

The safety endpoints are as follows for sub-study A and B:

- AEs
- Device deficiencies
- IOP
- Slit lamp examination findings including:
  - o Proportion of eyes with subjective posterior capsular opacification (PCO)
  - o Proportion of eyes with posterior capsulotomy
  - IOL observations

- Dilated fundus examination findings, including fundus visualization
- Intraoperative surgical problems
- Other procedures at surgery (combined and/or additional)
- SSIs

There are no safety hypotheses for either sub-study. The focus of the safety analysis will be a comprehensive descriptive assessment, of occurrence of ocular AEs and SSIs, as well as the other listed parameters. For all safety measures, descriptive statistics generated will be based upon the type of variable. For categorical variables summary statistics will include sample size, number in each category, and percentage in each category. For continuous variables, number of subjects/eyes, mean, median, standard deviation, minimum, and maximum will be reported. Safety measures may be presented in listings as appropriate.

All AEs occurring from the time a subject signs the informed consent form to study exit will be accounted for in the reporting. Safety analyses will be conducted using the safety analysis set on a treatment-emergent basis. Descriptive summaries (counts and percentages) and listings will be presented. Individual subject listings will be provided for AEs that occur after signing the informed consent form but prior to exposure to IP.

# 12.7 Interim Analyses and Reporting

The first interim analysis will be conducted when approximately 40 subjects (approximately 20 in each sub-study, minimum 30 subjects total) complete the 2-Month postoperative visit. This interim analysis is designed to review preliminary safety and effectiveness results for strategic business decision making purposes. There is no intention of stopping the study early. A second interim analysis will be conducted when all subjects complete the 2-Month postoperative visit, at this point treatment arms will be unmasked and all inferential analysis will be conducted. To control the overall type I error rate (at alpha = 0.05) the Lan-DeMets method with an O'Brien-Fleming alpha spending function will be utilized to distribute the type I error rate between the first and second interim analyses. The first interim analysis will be conducted when approximately 1/3 of the information fraction (in this case 1/3 of the target sample size) is available, therefore the alpha spend will be approximately 0.001 at the first interim analysis and accordingly the significance level at the second interim analysis (which is the primary inferential analysis point) will be 0.049 for all effectiveness endpoints. The power estimates provided below are based on a 0.049 significance level.

# 12.8 Sample Size Justification

A total of 132 subjects will be randomized (approximately 66 per sub-study). Assuming a drop-out rate of 10%, approximately 60 subjects will be evaluable at 2 months postoperative period (visit 3A) for each sub-study. The power estimates for each of the planned analyses are presented below:

Order	Endpoint	Comparison	Expected difference	Std. Dev^	Power	
Sub-study A						
Primary	Monocular BCDVA	NI	0	.08	>99.9%	
Sub-study B						
Primary	Monocular BCDVA	NI	0	.08	>99.9%	

Primary Monocular BCDVA NI 0 .08 >99.9%

^Estimate of std. dev is based on two recent Alcon studies (ILH297-C001 and ILI875-C002). \* Estimated based of simulated results from VirtIOL. \*\*Difference would indicate clinically meaningful effect. A NI margin of 0.1 logMAR is used for all non-inferiority comparisons above.

